8.2.4.10. Additional Safety

Listings of physical examination data, chest x-ray, and ECOG performance status will be provided.

8.2.5. Analyses of Patient Disposition Endpoints

Listings of violations of inclusion/exclusion criteria will be reported. This study will include the summaries of the numbers of patients who: sign the informed consent form (ICF), are screening failures, are enrolled, and are part of the full/evaluable analysis sets. The number of subjects discontinuing study participation, along with the reason, and descriptive statistics for the duration on-study (time from first dose to last contact) will also be calculated.

8.2.6. Analyses of Outcome Research Endpoints

All health outcomes analysis will be based on patients in the Full Analysis Set with available data.

The Outcomes Research endpoints are FACT-Leu overall, FACT-G overall, FACT-G subscales, Leukemia subscale (LeuS), and FACT-Leu Trial Outcome index. Univariate descriptive statistics will be used in the analysis of all the above endpoints.

For each of the endpoints listed above, summary statistics including Mean, Median, Standard Deviation, Minimum, Maximum, 95% CI will be reported at each time point. This will be done based on observed values as well as based on changes from baseline. A graphical display of the observed means over time for each of the endpoints will also be provided.

The above analyses will be done separately for each cohort and combined.

Appendix 1. CRITERIA TO IDENTIFY PHASE OF CML

Phase ^a	Findings
Blast Phase	
$\geq 30\%$ Blasts in blood or bone marrow Extramedullary Blasts proliferation, apart from spleen
 
If either of these 2 criteria is present, the patient is classified as Blast Phase regardless of other criteria.

Accelerated Phase	
$15\text{--}29\%$ Blasts in blood or bone marrow or $>30\%$ Blasts + Promyelocytes (with Blasts $<30\%$) in blood or bone marrow OR $\geq 20\%$ Basophils in blood OR Persistent platelets $<100 \times 10^9/L$ (not related to therapy) OR Clonal chromosomal abnormalities in Ph+ cells (CCA/Ph +), major route, on treatment

Chronic Phase	
$<15\%$ Blasts $<20\%$ Basophils $\leq 30\%$ Blasts + Promyelocytes (with Blasts $<15\%$) in blood or bone marrow
 
AND Platelets $\geq 100 \times 10^9/L$ (unless related to therapy)
 
AND No Extramedullary Blasts (except spleen)

^a Observance of any one criterion in the worse disease phase achieves that phase as the diagnosis (eg, 20% basophils alone elevates the diagnosis from CP to AP).

Appendix 2. DEFINITIONS OF HEMATOLOGIC, CYTOGENETIC, AND MOLECULAR RESPONSE

Response by Type	Definitions
Hematologic Complete (CHR)	WBC <10 x 10⁹/L Peripheral Blood Basophils <5% No Peripheral Blood myelocytes, promyelocytes, myeloblasts in the differential Platelet count <450 x 10⁹/L Spleen nonpalpable
Cytogenetic * Complete (CCyR) Partial (PCyR) Minor (mCyR) Minimal (minCyR) None (noCyR)	No Ph+ metaphases 1% to 35% Ph+ metaphases 36% to 65% Ph+ metaphases 66% to 95% Ph+ metaphases >95% Ph+ metaphases
Molecular Deep Molecular Response (MR4, MR4.5)	MR4= either (i) detectable disease with <0.01% BCR-ABL1^{IS} or (ii) undetectable disease in cDNA with >10 000 ABL1 transcripts MR4.5 =either (i) detectable disease with < 0.0032% BCR-ABL1^{IS} or (ii) undetectable disease in cDNA with >32,000 ABL1 transcripts in the same volume of cDNA used to test for BCR-ABL1. Ratio of BCR-ABL^{IS} ≤0.1%**.
Major (MMR)	

Abbreviations: CHR, complete hematologic response; CCyR, complete cytogenetic response, PCyR, partial cytogenetic response; Ph+, Philadelphia Chromosome positive; MCyR, major cytogenetic response; mCyR, minor cytogenetic response; minCyR, minimal cytogenetic response; noCyR, no cytogenetic response; MR4, MR4.5, deep molecular response; MMR, major molecular response.

*If bone marrow metaphases cannot be obtained or evaluated by chromosome banding analysis, the definition of CCyR (defined as <1% for FISH) may be based on interphase FISH of blood cells, provided that it is performed with Dual-Color Dual-Fusion or Dual-Fusion FISH probes and at least 200 nuclei are scored.

PCyR and CCyR are counted together and reported as MCyR.

**With ≥5,000 ABL1 transcripts.

Definitions of Hematologic Response for AP and BP CML*

CHR**	WBC \leq institutional upper limit of normal (ULN) ANC \geq 1.0 x 10⁹/L Platelet count \geq 100 x 10⁹/L BM Blasts \leq 5%*** No peripheral blood blasts or promyelocytes; Peripheral blood myelocytes + metamyelocytes $<$ 5%; Basophils in peripheral blood $<$ 5%* No evidence of extramedullary involvement
--------------	---

*The maximum % of basophils in peripheral blood was modified from <2 to $<5\%$ for a less restrictive constraint and alignment with the CHR criteria for CP CML patients according to ELN guidelines.

**If an on-treatment CBC is scheduled within 1 week from the last platelet transfusion or last dose of G-CSF, it should be considered "Not Evaluable" for hematological response assessment, and a CBC should be repeated at least 1 week from the last platelet transfusion or last dose of G-CSF received.

***CHR for AP/BP that the 5% BM blasts is only required when a BM differential is available.

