5.6.2. Permitted

- Any medication (other than those prohibited above) for a concurrent medical condition is permitted;
- Treatment of diarrhea and other gastrointestinal symptoms will be optimized (i.e., diarrhea will be monitored and managed using standards of care, including antidiarrheals, antiemetics, and/or fluid replacement). See [Appendix 4](#) for a sample Patient Information Card (Guidelines for the Management of Diarrhea);

- Palliative and supportive care for disease-related symptoms or toxicity due to study treatment;
- Treatment with growth factors [according to American Society of Clinical Oncology (ASCO) guidelines].²⁵ No prophylactic use of growth factors will be allowed;
NOTE: if an on-treatment BM assessment or CBC is scheduled within 1 week from the last dose of granulocyte colony-stimulating factor (G-CSF) or granulocyte-macrophage colony-stimulating factor (GM-CSF) growth factors, it should be considered “not evaluable” for response assessment, and a BM evaluation or CBC should be repeated at least 1 week from the last dose of growth factor;
- A short course of hydroxyurea or anagrelide for cytoreduction is allowed during the first month of treatment with bosutinib, provided that the last dose of hydroxyurea or anagrelide is stopped at least 72 hours before any CML disease assessment;
- Supplementation is advised for potassium levels or magnesium levels below the lower limit of normal, with consideration of the patient’s underlying renal function.

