7.1.1.2. Hematologic Response Assessment

Complete blood counts and differentials and extramedullary disease assessment (liver and spleen assessment) from the physical examination and bone marrow differentials will be used to determine response to treatment.

Hematologic responses must be of at least 4 weeks duration confirmed by 2 assessments at least 4 weeks apart. Complete hematologic response (CHR) and OHR (defined as CHR or RCP) will be evaluated by peripheral blood, and bone marrow differential (to define RCP) when available, only utilizing local laboratory results. Loss of hematologic response must be confirmed by 2 assessments at least 2 weeks apart. Note: if confirmation is lacking and the patient goes off treatment due to progressive disease, the assumption is that loss of hematologic response is confirmed for this study; therefore, the confirmation of loss of hematologic response 2 weeks apart is not required in this clinical context.

The definition of CHR for CP CML is outlined in [Appendix 11](#).

CHR for AP and BP CML is defined as white blood cell (WBC) count less than or equal to the institutional upper limit of normal (ULN); absolute neutrophil count (ANC) $1.0 \times 10^9/L$ or higher, platelet count $100 \times 10^9/L$ or higher; marrow blasts 5% or less with no peripheral blasts or promyelocytes; peripheral myelocytes + metamyelocytes less than 5%; basophils in peripheral blood less than 5%; and no evidence of extramedullary involvement.

Note: If an on-treatment CBC is scheduled within 1 week from the last platelet transfusion, it should be considered “Not Evaluable” for hematological response assessment, and a CBC should be repeated at least 1 week from the last platelet transfusion received.

Note: If an on treatment CBC is scheduled within 1 week from the last dose of G-CSF or GM-CSF growth factor, it should be considered “Not Evaluable” for response assessment and CBC should be repeated at least 1 week from the last dose of growth factor.

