Second, for the set of variables collected to derive peripheral blood or bone marrow differentials at each post-baseline visit up to week 13, if a given set are still incomplete, a non-missing set of lab variables obtained ± 3 days from the scheduled visit will be utilized to complete the derivation. For visits on or after week 13, a non-missing set of lab variables obtained ± 7 days of the visit will be utilized to complete that post-baseline assessment. The last non-missing peripheral blood or bone marrow differentials collected at week 1 day 1 or up to 30 days prior to week 1 day 1 will be used for baseline assessment. For example, if the bone marrow blast count was missing, the entire non-missing bone marrow assessment, not just the blast field, from another observation will be used. Some data handling rules for data combination are specified below.

- Data combination is needed only when the full dataset is not available on a single day at a given visit. The full dataset includes peripheral blood differential for chronic phase, and both bone marrow (when available) and peripheral blood differentials for advanced phase. The extramedullary assessment when absent should not preclude the derivation, and when present should be taken into account per response criteria rules.
- During the post-baseline data combination, the latest date will be used as the date of visit and the more conservative value will be taken if there is more than one measurement for a variable. For platelet counts, in case of multiple values, the lowest value will be taken. If any value falls above or below normal range, the out-of range value will be taken.

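### The SAP's evaluability rule for hematologic response is narrower than the protocol's, so assessments that the protocol calls not evaluable could be scored

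*SAP*

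**What the plan says.** **Protocol.** Section 7.1.1.2 has two notes on evaluability. One makes a CBC not evaluable within a week of a platelet transfusion. The other applies "If an on treatment CBC is scheduled within 1 week from the last dose of G-CSF or GM-CSF growth factor". Section 5.6.2 extends the growth-factor rule to marrow and asks that "a BM evaluation or CBC should be repeated at least 1 week from the last dose of growth factor". None of these notes is limited to a disease phase.

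**SAP.** The one counterpart is the double-asterisk footnote in Appendix 2, which begins "If an on-treatment CBC is scheduled within 1 week from the last platelet transfusion or last dose of G-CSF". Its marker sits on the CHR row under "Definitions of Hematologic Response for AP and BP CML". In the general response table, which holds the chronic-phase CHR definition, the same marker refers to the ABL1 transcript minimum. Appendix 1, which the SAP cites alongside Appendix 2 for hematologic response, has no evaluability note.

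**Derivation.** SAP 7 builds each hematologic assessment from recorded values. "The full dataset includes peripheral blood differential for chronic phase"; for advanced phase it also includes marrow when available. If the set is incomplete, values from within 3 days of the visit (before Week 13) or 7 days (from Week 13) are brought in. No check for transfusion or growth factor is mentioned there.

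**The concern.** A protocol instruction to treat a count as not evaluable does not remove that count from the database. If response is programmed from laboratory values, the exclusion has to be in the derivation rules, and there it is incomplete. A programmer cannot tell whether the narrower footnote is deliberate: protocol section 9 lets the SAP modify the protocol's plans, and the SAP gives no reason for the difference. There is no per-protocol set that might remove such records later.

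At stake are the primary confirmed OHR (analysed separately in AP and BP), the secondary OHR and CHR analyses, and best response. An altered count could create a response, bring its date forward, or hide a real one by interrupting the two successive responses needed for confirmation.

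**Working it through.** The documents state no figure that depends on this rule, so the check is a comparison of texts, followed by simple arithmetic.

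**1. Rules side by side** (exposure within the preceding week)

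| Assessment and exposure | Protocol, any phase | SAP, AP/BP CHR | SAP, chronic-phase CHR |
|---|---|---|---|
| CBC, platelet transfusion | not evaluable (7.1.1.2) | same | no rule |
| CBC, G-CSF | not evaluable (5.6.2, 7.1.1.2) | same | no rule |
| CBC, GM-CSF | not evaluable (5.6.2, 7.1.1.2) | no rule | no rule |
| Marrow, G-CSF | not evaluable (5.6.2) | no rule | no rule |
| Marrow, GM-CSF | not evaluable (5.6.2) | no rule | no rule |

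Five rules × two phase groups = 10 cells. The SAP carries 2, so 10 − 2 = 8 are missing. The cells do not weigh equally. Chronic-phase CHR contains no marrow criterion, so its two marrow cells cannot change CHR. A platelet transfusion cannot help chronic-phase CHR either, because that definition requires platelets below 450 × 10⁹/L.

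**2. Routes into the primary OHR (AP/BP)**

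- *GM-CSF.* A neutrophil count raised by GM-CSF could meet the AP/BP CHR floor of 1.0 × 10⁹/L. The same drug works against the WBC ceiling, so the net direction is not fixed.
- *Marrow combined across days.* A marrow taken on the same day as a CBC after G-CSF falls with that CBC. Combination can separate them. Illustration: last G-CSF on day 0, marrow on day 3, CBC at a visit on day 9 (Week 13 or later). The CBC is 9 days after G-CSF and evaluable. The marrow is 3 days after, which the protocol calls not evaluable. The gap to the visit is 9 − 3 = 6 days, inside the 7-day window, so SAP 7 would allow the marrow to be used.
- *RCP.* OHR is CHR or RCP. If the footnote is read as limited to CHR, a CBC excluded for CHR could still count towards RCP. The chronic-phase row of Appendix 1 has blast, promyelocyte, basophil and platelet criteria, and the platelet criterion carries an exception for therapy-related values. It has no WBC or neutrophil criterion, so those two counts cannot create RCP.

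**3. Route into chronic phase**

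Growth factor can raise WBC and immature cells, which chronic-phase CHR limits or forbids. Suppose CHR criteria are met at Weeks 4 and 13, and the Week 8 CBC was drawn after growth factor and fails. Scored as written, the sequence is yes, no, yes, and the two responses are not consecutive. With Week 8 set aside, they are (13 − 4) × 7 = 63 days apart and confirm each other. A later CBC can repair this, so the loss is permanent only when no later pair exists.

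**4. Size of one misclassification**

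The number of AP/BP patients is not given. Assuming n evaluable patients in a phase, one patient moves the rate by 100/n points: n = 5 gives 20, n = 10 gives 10, n = 20 gives 5. At n = 20, going from 10 to 9 responders moves the exact 95% interval from 27.2–72.8% to 23.1–68.5%.

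**5. Hydroxyurea and anagrelide**

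Protocol 5.6.2 allows a short first-month course "provided that the last dose of hydroxyurea or anagrelide is stopped at least 72 hours before any CML disease assessment". That is a condition of use, and exclusion criterion 3 is its baseline counterpart. Neither calls a count not evaluable. The scheduled CBCs at Weeks 1 to 4 span 28 − 7 = 21 days, or 23 with the ±1 day windows. Confirmation needs 28, so two of these CBCs cannot confirm each other. An affected count could only be the first of a pair, with a qualifying count at Week 8 or later.

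**The case against.** The best defence is that this is a wording mismatch with little effect. SAP version 2.0 was written to align with Amendment 1, silence is not a stated modification, and the protocol still tells sites to treat such assessments as not evaluable and to repeat them. Prophylactic growth factor is prohibited and transfusion is restricted. Most endpoints are cumulative over many counts, so one bad value rarely decides a patient's status. The footnote speaks of hematological response assessment in general, so applying it to RCP is a natural reading.

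Much of this stands: altered counts *could* enter, not *will* enter, and the frequency may be low. But GM-CSF and marrow are absent on any reading, and SAP 7 leaves the borrowed sets unchecked. SAP 7's rule to take the lowest platelet value helps only when several values are combined. The footnotes below the AP/BP table in protocol Appendix 11 were not in the text available to me. If they match the SAP's, the mismatch also lies within the protocol and still needs resolving.

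A reader might also infer more than the documents support:

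- *Transfused platelets or G-CSF counts freely create AP/BP CHR.* The footnote already excludes those CBCs.
- *The SAP dropped a 72-hour evaluability rule.* The protocol has none.
- *The chronic-phase gap affects the primary endpoint.* OHR is confined to AP and BP.
- *Response could be wrongly scored as lost.* The SAP has no duration endpoint for hematologic response, and PFS uses investigator-assessed progression recorded on the CRF.
- *Some 10–25% of patients are exposed.* The pooled Grade 3/4 rates of 25.4% (thrombocytopenia) and 11.5% (neutropenia) are adverse-event frequencies, not use of transfusion or growth factor.

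**Conclusion.** The concern holds as a conflict between a stated SAP rule and the protocol. Programmed as written, the SAP could score assessments that the protocol calls not evaluable. In AP/BP this could affect the primary OHR, mainly through GM-CSF, marrow combined across days, and RCP if the footnote is taken as limited to CHR. In chronic phase it reaches only secondary confirmed CHR, and best response where CHR is the highest category attained. The direction is mixed. The number of affected assessments cannot be estimated from the documents, and the 5 to 20 points per patient rests wholly on the assumed 5 to 20 evaluable patients in a phase. The study is descriptive, so no test or decision rule is affected. The case for acting is that the correction is cheap and a small AP or BP group is sensitive to a single patient.

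**What to change.** State in SAP 7, with a matching note in Appendices 1 and 2, that for all phases and for CHR, RCP and OHR:

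- a CBC within 1 week after a platelet transfusion, G-CSF or GM-CSF is not evaluable;
- a marrow within 1 week after G-CSF or GM-CSF is not evaluable;
- such records are skipped when judging whether two responses are consecutive;
- such records are not used as borrowed sets in the ±3 or ±7 day combination.

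For hydroxyurea and anagrelide, at most flag assessments within 72 hours of use and repeat the analysis without them as a sensitivity analysis.

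The cost is SAP wording and a merge with CRF data. Protocol 5.6 already requires transfusions and growth factors to be recorded; I assume usable dates are among the fields. SAP 7 sets a stop date with a missing day to the end of the month, so the text should say whether that convention applies here, since it would widen the exclusion. The downside is that a few assessments become not evaluable, and a patient left without a confirmed response would count as a non-responder.
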